**Using fMRI-guided TMS to Increase Central
Executive Function in Older Adults
(MCI_Sub)**

NCT04176406

This document includes the study protocol and the statistical plan approved on March 1st 2020.

Study Protocol:

This experimental supplement is focused on applying TMS to a cortical network node in 30 patients diagnosed with MCI or found to be at risk for cognitive impairment (This cohort will be referred to as "MCI patients", but includes subjects with diagnosed MCI and subjects not currently diagnosed, but at risk for cognitive impairment as defined by criteria below). This blinded, sham-controlled trial will feature a mixed model 2 x 3 x 2 x 2 cross-over design, with rTMS Type (active, sham), Difficulty Level defined by accuracy (easy, medium, hard levels), Stimulation Location (Network, Activity target), and Group (healthy OAs, MCI) as factors. As such, this design reflects the fact that all subjects receive both active and sham rTMS applied to up to two different scalp locations during a WM task at up to three levels of difficulty. Study procedures are listed in **Table 3**. Thirty healthy OAs (age range: 55-80 years) and thirty MCIs (age range: 55-80 years) will participate. In the first session, which will take about 2 hours, participants will be consented and screened for the study, submit a saliva sample for genetic testing, determine TMS motor threshold, and then learn and practice the WM task. The next visit will involve a structural MRI and fMRI recorded from both groups while they perform the WM task. Cortical locations within the FPN (Network target) and DLPFC (Activity target) will be used as targets for rTMS will be chosen from an analysis of subject-specific fMRI activations from the WM task completed in this MRI Session. This session, which will last up to 3 hours, will be followed by up to four sessions of rTMS + MRI, each lasting about 3 hours. These rTMS+MRI sessions will begin ~1 week after the MRI Session, to allow for time to process the imaging data. rTMS+MRI sessions (involving active or sham rTMS and Network or Activity targets) will use coil locations and rTMS device intensities based on realistic head modeling the MRI will collect structural and resting state information.

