the individualized target region, based on the cortical site with the highest computed controllability (Network target) or parametric activity (Activity target), using a MagVenture stimulator. Neuronavigation (BrainSight, Rogue Research, Canada) and a robot (SmartMove, ANT, Netherlands) will be used to optimize the targeting. Brain atrophy could also reduce TMS effectiveness because it increases the distance between scalp and the cortex but this potential confound is addressed by adjusting TMS intensity using the E-field computation. In visits 3 to 6, participants will perform the Working Memory Task while active or electrical sham stimulation is delivered using an A/P Cool-B65 coil (MagVenture, Denmark). In a stimulation trial, twenty-five pulses of 5Hz rTMS will be delivered at 100% of the effective E-field. Sham rTMS will be administered with a sham coil equipped with shielding to block magnetic field output but retain the auditory and some of the tactile aspects of active stimulation. This method reproduces the somatosensory sensations as the magnetic field stimulates scalp muscles, and produces the same acoustic artifact than the active stimulation, without inducing current in the cortex⁵⁹.

DWI Structural Connectivity. *Whole-brain tractography.* As in our prior DWI tractography work, Dipy⁶⁰ will be used to generate connectomes representing structural connections between all cortical regions in the Harvard-Oxford Atlas. For structural connection matrices, network edges are defined by the number of tractography streamlines between all nodes of the target network.

Event-related fMRI analyses, functional connectivity and graph theory measures. The Frontoparietal network (FPN) is identified by standard atlas⁶¹, and will be validated with voxelwise independent component analysis (ICA). Task-related connectivity is measured using beta-series correlations²⁰, which estimates a time-series by examining region-by-region interactions that are modulated by task conditions. SMEs for activity and connectivity will be analyzed with a Group (healthy OAs vs. MCIs) x Targeting (Network-based vs. Traditional) x Stimulation (Active vs. Sham) ANOVA using SPM⁶². All matrices are evaluated for descriptive graph-theoretical properties (including degree and controllability) using the Brain Connectivity Toolbox.

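### The only stated active-versus-sham model has no session (period) term, although the task is repeated over up to six visits: a small precision cost and a cheap improvement

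*Combined protocol and SAP*

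**What the plan says.** The opening of the Study Protocol describes a cross-over in which every subject receives active and sham rTMS at up to two targets. At the first visit participants "then learn and practice the WM task". Then "The next visit will involve a structural MRI and fMRI recorded from both groups while they perform the WM task". That visit is "followed by up to four sessions of rTMS + MRI". TMS methods adds: "In visits 3 to 6, participants will perform the Working Memory Task while active or electrical sham stimulation is delivered".

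The design factors are rTMS type, difficulty, "Stimulation Location (Network, Activity target), and Group (healthy OAs, MCI) as factors". The model for active versus sham is in the section on event-related fMRI analyses, functional connectivity and graph theory measures. It crosses Group and Targeting with "Stimulation (Active vs. Sham) ANOVA using SPM", and its outcomes are SMEs for activity and connectivity. The abbreviation SME is not expanded.

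The Statistical Plan adds a Greenhouse-Geisser correction, k-fold cross-validation (both under Analytical Rigor) and gender as a covariate (under Consideration of sex as a biological variable). None of these is a session term. The opening section also says "Study procedures are listed in" Table 3, which is not in the supplied text.

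**The concern.** In a cross-over, calendar position is the natural competitor to the treatment contrast. People improve with practice, tire, or get used to the scanner, and such drift falls on whichever condition comes later. A session term takes the drift out of the residual error. If orders differ between subjects but are not balanced, it also takes the drift out of the active-versus-sham estimate. Without the term, drift stays in the error at best and enters the estimate at worst. Greenhouse-Geisser does not help, because it deals with unequal variances of differences and not with a shift in means over time.

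**Working it through.** **No plan figure to reproduce.** The documents give no drift, no within-subject SD and no session effect. The power statement (average power 0.8, N = 80) does not involve session. Its four repeated measurements are defined as two groups by two targeting methods, so they are not evidence of four stimulation sessions and are not used here.

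**Task exposures.** One practice visit, one MRI visit and up to four rTMS visits give 1 + 1 + 4 = up to 6 visits with the task, 5 of them after practice.

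**Where a session term could appear.**

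| Place | Terms named | Session? |
|---|---|---|
| Study Protocol, design factors | rTMS type, difficulty, location, group | no |
| Event-related fMRI analyses | Group, Targeting, Stimulation | no |
| Analytical Rigor | Greenhouse-Geisser, k-fold | no |
| Consideration of sex | gender | no |

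**Inputs for size.** N = 30 + 30 = 60 (Study Protocol). Assumed: all four sessions completed (2 active, 2 sham), within-subject SD set to 1, and linear drift of b SD per session with b from 0 to 0.3.

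**Standard error without drift.** Per subject, active minus sham has variance 1/2 + 1/2 = 1, so SE = sqrt(1/60) = 0.1291.

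**Random order, no session term.** The two active sessions can fill four positions in six ways. The difference in mean position is then -2, -1, 0, 0, 1 or 2, with mean square (4 + 1 + 0 + 0 + 1 + 4)/6 = 1.667. The SE is multiplied by sqrt(1 + 1.667 b²). The same factor applies to Targeting and to the interaction of Targeting with Stimulation.

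**Random order, session term added.** Simulating random orders for 60 subjects gives an SE of about 0.130 whatever the drift, about 1% above 0.1291.

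| b | factor without session | SE without session | SE with session |
|---|---|---|---|
| 0 | 1.000 | 0.129 | 0.130 |
| 0.1 | 1.008 | 0.130 | 0.130 |
| 0.2 | 1.033 | 0.133 | 0.130 |
| 0.3 | 1.072 | 0.138 | 0.130 |

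The term therefore breaks even near b = 0.1 and gains beyond that. With a position-balanced order it costs no SE (0.1291).

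**Subjects with one target.** With two sessions in random order, the difference has variance 2 and the position difference is ±1. The factor is sqrt(1 + b²/2) = 1.010 at b = 0.2.

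**Effect on power.** Read the plan's smallest interaction effect, 0.7, in within-subject SD units (an assumption). The Stimulation main effect then has power 0.9996 at b = 0 and 0.9987 at b = 0.3. Group by Stimulation has SE sqrt(2/30) = 0.258 and power 0.76, falling to 0.73 at b = 0.2 and 0.70 at b = 0.3.

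**If order were unbalanced (illustration only).** Suppose 40 of 60 subjects were sham-first. Bias is b(40 - 20)/60 = b/3 if conditions alternate, and 2b/3 if both sham sessions precede both active ones. At b = 0.2 a 5% test of no effect rejects about 7.5% or 14% of the time without a session term, and about 5% with one. Nothing in the documents supports this split.

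**The case against.** The strongest reply is that the harm depends on facts the documents do not give. A reader might infer that practice biases active versus sham, or that session order was left to chance or convenience. The text supports neither reading. It does not state the order, Table 3 may, and under random or balanced order the estimate is unbiased. What remains is a loss of 0 to 7% in SE that rests on assumed drift, and it hardly matters for the Stimulation main effect at the plan's own effect sizes. This stands, and it is why the point is minor.

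The link from task practice to the quoted model is also weaker than it looks. If SME means a subsequent-memory effect, which the long-term memory test in the Working Memory task section makes plausible, it is a contrast within a session. A uniform practice shift then cancels, and only drift in the SME itself matters. "Difficulty Level defined by accuracy" and two earlier exposures may flatten drift further. The Study Protocol also says that MRI at the rTMS visits collects structural and resting-state scans, so it is unclear how many task-fMRI sessions per subject enter the model. These points stand as limits on size. They do not supply a session term, and the gap applies wherever active and sham sessions are compared.

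Finally, one might go on to require an elaborate mixed model. The plan does not propose the random-intercept-only model that such a requirement would correct. Its Greenhouse-Geisser correction already implies a repeated-measures analysis.

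**Conclusion.** The omission is real and the point is minor. The single stated stimulation model lacks a session term, and no other part of the supplied text adds one. Under fully random order the supported cost is an SE increase of about 1%, 3% or 7% at an assumed linear drift of 0.1, 0.2 or 0.3 within-subject SD per session, and none at zero drift. These figures assume 60 subjects with all four sessions, and the cost is smaller for one-target subjects. Bias in active versus sham is possible only if order is unbalanced across subjects; it is not shown and not claimed. If all subjects shared one order, a full session factor could not be separated from the treatment contrasts and no model would repair it, so the order is worth confirming.

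**What to change.** 1. Add session number, as a categorical within-subject term, to every comparison of active with sham sessions: fMRI activity, connectivity and any behavioural summary. Keep the repeated-measures error strata that the plan implies. No random-slope structure or particular degrees-of-freedom method is needed for this purpose.
2. Confirm that the session order in Table 3 is randomised or position-balanced within each Group, and state it in the statistical plan. No particular list of sequences is required.
3. State which sessions supply task-fMRI data to the model.
4. If per-subject contrast images are taken to a second level with effect-coded sequence in place of a session term, limit this to a small balanced set of sequences. With all 24 orders and 60 subjects, about 22 orders occur and the Stimulation SE rises from 0.129 to about 0.150 (16%), against about 0.130 with a session term.

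Cost: a sentence or two of SAP wording, up to 3 within-subject degrees of freedom (of 180 with complete data), and about 1% in SE if order is random and there is no drift.

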E-field Modeling. In order to determine the *intensity* of network-based targeting, we will use electric field (E-field) modeling. The BSEL lab has extensive experience with the creation of anatomically realistic E-field models of transcranial electric and magnetic stimulation in humans, which have been applied to healthy OA populations in ongoing NIH-funded projects by Co-I's [name] and [name] (U01-AG050618), using SimNIBS software⁶³. A detailed model of the TMS coil is combined with a detailed head model. Isotropic tissue conductivities are assigned to the various tissue compartments. Critically, this method will also include anisotropic conductivity in the white matter based on the DWI data. We will carry out E-field simulations over a range of coil orientations and tilts to predict maximal activation of the FPN. The target node (i.e., the node with the highest controllability, identified above) will be used as the center of a 3×3 grid for positioning the coil in simulations of the E-field corresponding to these 9 coil positions and 6 orientations (54 combinations). The simulation E-field maps will be extracted and correlated, voxel-to-voxel, with the fMRI activation and the simulation that yields the highest correlation is selected as the target coil position and orientation.

Statistical Plan:

Power analysis. Our labs have considerable experience with combining neurostimulation and neuroimaging. Through the parent award we have enrolled 85 individuals in multiday memory protocols and results from these data reflect the size of potential future TMS effects. Power calculations were therefore conducted in R software (R Development Core Team, 2016) using the repeated-measures ANOVA module. With N=80 subjects, in a mixed-effects design consisting of 4 repeated measurements per subject (2 groups x 2 TMS targeting [network-based, traditional targeting]), Cohen's $d = 0.9$ for each of the main effects, with interaction effects between 0.7-0.9, attaining an average power of 0.8 at an overall significance level of 5%.

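### Does describing the E-field coil search only for the Network target undermine the Network-versus-Activity comparison?

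*Combined protocol and SAP*

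**What the plan says.** The opening design paragraph of the Study Protocol lists the factor as "Stimulation Location (Network, Activity target"). It introduces the sites as "Cortical locations within the FPN (Network target) and DLPFC (Activity target") and, in a sentence that is grammatically broken, says that they "will be chosen from an analysis of subject-specific fMRI activations from the WM task completed in this MRI Session". It adds that the stimulation sessions ("involving active or sham rTMS and Network or Activity targets) will use coil locations and rTMS device intensities based on realistic head modeling").

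TMS methods gives a separate criterion for each target: stimulation is "based on the cortical site with the highest computed controllability (Network target) or parametric activity (Activity target").

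E-field Modeling opens with the intensity "of network-based targeting, we will use electric field (E-field) modeling". It then turns to placement: "The target node (i.e., the node with the highest controllability, identified above) will be used as the center of a" 3×3 grid, with 9 positions and 6 orientations, and the simulated field maps are "correlated, voxel-to-voxel, with the fMRI activation and the simulation that yields the highest correlation is selected as the target coil position and orientation". It does not name the fMRI contrast, the mask or the grid spacing, and it does not mention the Activity coil.

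The ANOVA in the section on event-related fMRI analyses and the Power analysis both label the two levels network-based and traditional. Neither defines traditional.

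**The concern.** Three things seem not to fit together. First, the design paragraph appears to take both sites from task activation, whereas TMS methods takes the Network site from controllability. Second, the design paragraph says coil locations are modelled for either target, whereas the only search described is centred on the Network node. Third, the factor is called a location in one place and a targeting approach in two others.

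What would be at stake is how the targeting factor is interpreted. Suppose only the Network coil had its pose optimised. The two levels would then differ in site and also in how well the coil is placed. The sham sessions would not remove this: the plan says sham induces no cortical current, so a gain from better placement would exist only under active stimulation and would appear as a Targeting by Stimulation interaction. Suppose instead that both coils were fitted to the same task map. The final placements might then lie closer together in some subjects, which would weaken the contrast.

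**Working it through.** **Site of the Network target.** TMS methods picks the node by controllability. E-field Modeling takes that same node, described there as already identified, as the centre of its grid. These are two steps of one procedure: controllability fixes the neighbourhood, and the fit to the fMRI map ranks coil poses within it. A node alone does not fix position, tilt and orientation, so a second criterion is needed. The only text in tension with this is the overview sentence in the design paragraph, whose grammar has broken down. The two detailed sections agree with each other.

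**Pose of the Activity coil.** The design paragraph says coil locations come from head modelling in sessions with either target. TMS methods gives the Activity site (parametric activity) and applies neuronavigation and the robot without distinguishing targets. E-field Modeling writes the search out for Network only, but does not exclude Activity. That only Network is searched is therefore an inference from silence, set against an express statement. What is missing is the detail of the Activity search.

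**Intensity.** The design paragraph covers both targets. TMS methods says intensity is informed by E-field modelling and adjusted by the E-field computation, again with no limit by target. Only the opening phrase of E-field Modeling is narrower.

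**Label.** Even in the design paragraph the levels are named by how the target is chosen (Network, Activity). The other two sections use targeting. Nothing in the ANOVA changes with the label.

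**The plan's own figure.** 3 × 3 = 9 positions; 9 × 6 orientations = 54. This reproduces.

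**How large could it be?** The documents give no gain from the search, no distance between targets and no share of subjects whose placements coincide. All such values below are assumed. The sample is 30 + 30 = 60, assuming every subject receives both targets, although the plan allows up to two locations and up to four sessions. Tests are two-sided at 5%.

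*Only Network searched, no true site effect.* Paired t test with noncentrality d√60:

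| Assumed gain g | d = g (SD of the contrast itself) | d = 0.707g (single-session SD, correlation 0.5) |
|---|---|---|
| 0.2 | 33% | 19% |
| 0.3 | 63% | 37% |
| 0.4 | 86% | 58% |

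The last column follows from the mechanism in the concern: the gain is present in one of the four sessions. For the targeting main effect the mean is g/2 and the SD is √(1 − 0.5) = 0.707, so d = 0.707g. For the interaction the mean is g and the SD is √(4 × 0.5) = 1.414, which gives the same d. The rejection rate depends on a gain nobody has measured and on the scale chosen for it.

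*Both searched, a share f of subjects coinciding.* The effect shrinks to d(1 − f). For Group by Targeting with 30 per group and the planned interaction range d = 0.7 to 0.9:

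- f = 0: power 0.76 to 0.93
- f = 25%: d = 0.525 to 0.675, power 0.52 to 0.73
- f = 50%: d = 0.35 to 0.45, power 0.27 to 0.40

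The targeting main effect at d = 0.9 keeps power of 0.93 even at f = 50%. The 0.76 at f = 0 reflects the group size, not coil placement. No document figure supports any f above zero, and the search is local, around a node chosen separately.

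**The case for a change.** The best case for acting is that targeting is a factor in the planned ANOVA and in the power calculation, so a reader should be able to tell what its two levels are. E-field Modeling defines its grid centre explicitly as the controllability node, and silence about the other level of a two-level factor is itself an ambiguity. The plan commits to COBIDAS reporting and to replicability, and nobody can replicate a placement rule that is written for one coil only. Clarifying the text would be cheap.

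Most of this stands as a remark on drafting. The passages do not line up, and traditional is undefined. It does not show a flaw in the comparison. If the two targets pass through the same steps, the contrast is between sites. If they do not, it is between two complete procedures, which is what the labels in the ANOVA and Power analysis suggest and which is a legitimate question. In either case the data collected and the ANOVA fitted are the same. The COBIDAS commitment also leads the team to report what was done for each coil.

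A further proposal would be to record the overlap between final placements and adjust for it or exclude subjects on it. This addresses a convergence the documents do not show, would need a threshold for which they give no basis, and would cost sample size in a study of 60 that the plan itself calls exploratory.

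**Conclusion.** No change is needed. The plan leaves one placement step unwritten for the Activity coil, has one broken overview sentence and uses two names for one factor. A team running the trial settles these in its targeting procedure and reports them in its methods. When results are written up, a targeting or Targeting by Stimulation effect should be attributed to site or controllability alone only if both coils went through the same placement steps; otherwise it compares two whole procedures. That is ordinary care in interpretation and needs no amendment.

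Active versus sham within one target is not biased under any reading. The effect on the targeting contrast cannot be sized from the documents: the 19% to 86% rejection rates and the loss of interaction power rest wholly on assumed gains, overlaps and correlations. This conclusion takes the controllability step and the E-field search as consecutive, and takes the design paragraph at its word that modelling covers both targets. Which placement rule is correct is for the sponsor to say.

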Imaging acquisition and preprocessing. Three forms of structural images will be acquired: **1) full-brain high-resolution T₁-weighted structural images** (inversion recovery prepared 3D SPGR) with full coverage of the head and neck, (TR = 500ms; TE = 20ms; FoV = 24cm²; image matrix = 256x256; voxel size = 0.94 x 0.94 x 1mm), and **2) echo-planar (EPI) sensitivity encoding (SENSE) DWI images** with the same orientation (TR = 2000 ms; FoV = 24 cm²; image matrix = 128²; voxel size 0.94 x 0.94 x 1 mm; b-value = 1000 s/mm²; 1 repetition; 36 diffusion-sensitizing directions). In addition, two forms of functional images will be collected: 1) for **resting state EPI** functional imaging data, which will be used to estimate RSFA, we will acquire 24 slices parallel to the AC-PC plane using a BOLD-sensitive gradient-echo sequence with EPI k-space sampling, at TR of 2s (TE: 35ms; FOV: 25.6cm; voxel size: 63mm), and 2) **event-related EPI**, which uses the same scan parameters and will measure the global reactivity to our Working Memory Task.

TMS methods. Coil targeting will be achieved using frameless stereotaxy (BrainSight: Rogue Research, Montreal). TMS is applied with a figure 8 coil based on 100% resting motor threshold (rMT)⁵⁸, though TMS intensity will also be informed by E-field modeling (described below). TMS will be delivered consecutively over

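### Is stimulation intensity given two conflicting definitions, with the E-field procedure covering only the Network target?

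*Combined protocol and SAP*

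**What the plan says.** Four places bear on intensity.

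- **Study Protocol, opening paragraph.** In the first session the team will "determine TMS motor threshold, and then learn and practice the WM task". The stimulation visits that follow cover both targets; they are described as "involving active or sham rTMS and Network or Activity targets) will use coil locations and rTMS device intensities based on realistic head modeling".
- **TMS methods, first part.** "TMS is applied with a figure 8 coil based on 100% resting motor threshold (rMT"), and the sentence goes on: "though TMS intensity will also be informed by E-field modeling (described below").
- **TMS methods, continued.** The section raises atrophy as a threat: "Brain atrophy could also reduce TMS effectiveness because it increases the distance between scalp and the cortex". Its answer follows directly, namely that "this potential confound is addressed by adjusting TMS intensity using the E-field computation". On what each trial delivers, it says that "twenty-five pulses of 5Hz rTMS will be delivered at 100% of the effective E-field". The document uses the last term once and does not define it.
- **E-field Modeling.** The section says its purpose is to set the intensity of network-based targeting. It centres a 3×3 grid on the node with the highest controllability, crosses the 9 positions with 6 orientations, and compares the 54 simulated fields with the fMRI map. The fields are "correlated, voxel-to-voxel, with the fMRI activation and the simulation that yields the highest correlation is selected as the target coil position and orientation".

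Group, Targeting and Stimulation are the three factors of the planned fMRI ANOVA.

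**The concern.** A reader who wants to know how device output is set meets two reference quantities, motor threshold and an undefined field, and is sent to E-field Modeling for the link. That section announces intensity but describes only a search over coil placement. Its grid is centred on the Network node, and no grid is described for the Activity node. It also mentions coil tilts without saying whether the 6 orientations include them.

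Two contrasts could be affected.

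- **Group.** The protocol itself names atrophy as a threat to TMS effectiveness and answers it with an intensity adjustment that cannot be traced in the text. If no adjustment were made, the comparison of healthy older adults with the MCI group could carry a dose difference.
- **Targeting.** If only Network sessions had modelled intensity and a placement search, a difference between Network and Activity would mix choice of site with quality of procedure.

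The statistical plan lists no summary of delivered intensity from which a reader could judge either.

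**Working it through.** **1. The plan's own figure.** The 3×3 grid gives 9 positions, and 9 × 6 orientations = 54, as stated. The 54 candidates differ only in position and orientation, so tilt is either part of the 6 orientations or not simulated. This is a point of wording.

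**2. Can the selection rule return an intensity?** For a fixed placement, the modelled field E scales with device output. For any c > 0 and activation map f,

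r(cE, f) = c·cov(E, f) / [c·sd(E)·sd(f)] = r(E, f).

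A numerical check on 54 arbitrary simulated maps, with the field multiplied by 0.5, 0.8, 1.0, 1.2 and 2.0, selected the same map each time with the same r (0.025696). The rule therefore cannot set intensity. But the section says only that the correlation selects position and orientation, so this confirms an omitted step and exposes no error.

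**3. Do the two intensity statements conflict?** They would if one fixed output at exactly 100% of threshold in everyone (a ratio of output to threshold of 1.00) while the other adjusted for atrophy, because any non-zero adjustment moves the ratio off 1.00. The document does not state that rule. It describes intensity as based on threshold and, in the same sentence, as also informed by modelling. The opening paragraph and the atrophy sentence likewise say that modelling affects intensity. All the statements are compatible with a threshold-based value modified by the head model. The formula for the modification is what is absent.

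**4. Is the Activity target left out?** E-field Modeling describes 54 candidates for the Network node and none for the Activity node. The opening paragraph says that sessions at either target use modelled coil locations and modelled intensities. Nothing in E-field Modeling excludes the Activity target. To conclude that only Network sessions are modelled, one must set the opening paragraph aside. What is not written out is the centre of the Activity grid.

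**5. What would a report of delivered intensity add?** Inputs: 30 subjects per group (Study Protocol) and an assumed between-subject SD of 10–15% of the mean; the documents give no SD.

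- Group gap, 95% half-width: t(58) × √(1/30 + 1/30) = 2.002 × 0.2582 = 0.517 SD, or 5.2–7.8% of the mean.
- Network–Activity gap, at most 60 subjects: 2.001/√60 = 0.258 × SD of the within-subject difference, where SD_diff = SD × √[2(1 − ρ)] and ρ is the correlation between a subject's two intensities:
  - ρ = 0: 0.365 SD, or 3.7–5.5% of the mean
  - ρ = 0.5: 0.258 SD, or 2.6–3.9%
  - ρ = 0.9: 0.116 SD, or 1.2–1.7%

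These figures describe the precision of a descriptive table. They do not measure bias in any planned result, and no term in the ANOVA would change.

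**The case for a change.** The best case for a change is that TMS methods sends the reader to E-field Modeling for the intensity step, that section is present and complete, and the step is not in it. The assurance about atrophy therefore rests on something the plan does not contain. Stating an intention for both targets is not the same as describing a procedure for both. Defining one term and adding one table would cost little.

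The textual part stands: the term is undefined, the written rule returns only placement, and the written grid belongs to the Network node.

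The consequences do not follow. No difference in dose between groups or targets is shown. Active and sham stimulation are compared within subjects, and nothing suggests that their intensities differ at a given target. The exposed contrasts are Group, Targeting and their interactions, in a study that calls itself exploratory.

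A table of output or modelled field by Group and Location would also be hard to read:

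- Pooled over sham sessions, it would not describe delivered dose, because the sham coil is shielded.
- Similar fields in the two groups would not show that an adjustment was made, since similar atrophy would give the same picture.
- Different absolute fields would not show a failure if the reference field is individual. Treating equality as the aim presumes the very rule that is the sponsor's to set.

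**Conclusion.** The concern identifies incomplete specification, not two conflicting rules. The investigators plan head modelling for both targets and measure motor threshold in the first session. They cannot run a stimulation session without turning these into a device setting, so the gap is one they must fill in practice and can fill sensibly. Writing the step down would make the text easier to follow, but it would not alter the design, the ANOVA or its error rates.

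The size of any effect on results is not computable from the documents, and none is claimed. The conclusion rests on two readings: that the opening paragraph's commitment to modelled locations and intensities at both targets governs, and that threshold-based means a starting value and not a fixed output. Both are the natural sense of the text. If Activity sessions were in fact run without modelling, the Network–Activity contrast would have to be interpreted with that in mind, but nothing in the plan says so. No view is taken on which intensity rule is right.
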